8.5.2 Restricted concomitant medications and therapies

(1) Iron supplements

From the first day of the screening period to completion of blood sampling for haematology tests on the final day of the treatment period, administer iron supplements to maintain serum ferritin values of ≥ 100 ng/mL or TSAT of $\geq 20\%$. Iron supplements may be omitted for subjects who respond poorly to them, such as those with an allergy or those with adverse drug reaction (ADRs) to iron (vomiting, etc.).

Investigators/subinvestigators will determine iron supplement dosage and administration route.

Important: Oral iron supplements may impair MT-6548 bioavailability, so oral iron supplements must not be taken at the same time as MT-6548 Tablet. Subjects taking oral iron supplements will be instructed not to take any within 2 hours before or after taking MT-6548 Tablet.

(2) Iron-containing phosphate binders (ferric citrate hydrate, sucroferric oxyhydroxide)

New use of iron-containing phosphate binders is fundamentally prohibited from the first day of the screening period to completion of blood sampling for haematology tests on the final day of the treatment period. If iron-containing phosphate binders are used by a subject on the first day of the screening period, then the same dosage of the same type should fundamentally be continued from the first day of the screening period to completion of blood sampling for haematology tests on the final day of the treatment period. If investigators/subinvestigators determine that a dosage increase is required for iron-containing phosphate binders, then additional treatment will be performed with hyperphosphatemia drugs containing no iron, or treatment switched to hyperphosphatemia drugs containing no iron. Dosage of iron-containing phosphate binders may also be reduced if determined necessary according to the subject's condition. Switching to another hyperphosphatemia drug containing no iron will not be permitted during the period from the first day of the screening period to completion of designated tests for treatment period Week 4.

Important: As with oral iron supplements, iron-containing phosphate binders may impair MT-6548 bioavailability, so iron-containing phosphate binders must not be taken at the same time as MT-6548 Tablet. Subjects taking iron-containing phosphate binders will be instructed not to take any within 2 hours before or after taking MT-6548 Tablet.

(3) Hemodialysis

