10.1.2 Other endpoints

The following endpoints will also be studied.

- (1) Changes from baseline in mean Hb levels at Weeks 20 and 24 of the treatment period
Changes from baseline in mean Hb levels at Weeks 20 and 24 of the treatment period will be calculated.

- (2) Proportion of subjects with a ≥ 1.0 g/dL increase from baseline in mean Hb levels at Weeks 20 and 24 of the treatment period
Proportion of subjects with a ≥ 1.0 g/dL increase from baseline in mean Hb levels at Weeks 20 and 24 of the treatment period will be calculated
- (3) Ratio of subjects who received ESA rescue therapy
Ratio of subjects who received ESA rescue therapy from the first day of the treatment period to treatment period Week 24 will be calculated.
- (4) Ratio of subjects who received red blood cell (RBC) transfusion rescue therapy.
Ratio of subjects who received RBC transfusion from the first day of the treatment period to treatment period Week 24 will be calculated.
- (5) Study drug dosage
Mean daily dosage will be calculated for each scheduled study visit from the first day of the treatment period up to treatment period Week 24.
- (6) Total number of study drug dosage adjustments
The total number of dosage adjustments from the first day of the treatment period to treatment period Week 24 will be calculated.
- (7) Quantity of iron administered
Mean weekly dosage will be calculated for each scheduled study visit from the first day of the treatment period up to treatment period Week 24.
- (8) Ratio of subjects with serum ferritin of ≥ 100 ng/mL or TSAT $\geq 20\%$.
Ratio of subjects with serum ferritin of ≥ 100 ng/mL or TSAT $\geq 20\%$ at each evaluation timepoint will be calculated.
- (9) Change from baseline of iron-related measures (serum iron, TIBC, TSAT, and serum ferritin) and hepcidin.
Changes in iron-related measures (serum iron, TIBC, TSAT, and serum ferritin) and hepcidin from baseline will be calculated for each evaluation timepoint.
- (10) Change from baseline of haematocrit, RBC count, reticulocytes (counts and fractions), and EPO.
Changes in haematocrit, RBC count, reticulocytes (counts and fractions), and EPO from

baseline will be calculated for each evaluation timepoint.

(11) QOL measures (EQ-5D-5L, KDQOL)

Scores for QOL measures will be calculated for each evaluation timepoint.

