13.3.2 Efficacy

(1) Analysis methods for primary endpoint

1) Mean Hb at treatment period Weeks 20 and 24

For mean Hb at treatment period Weeks 20 and 24, mean Hb at each timepoint will be modeled using MMRM with the following model, and mean Hb at treatment period Weeks 20 and 24 and their two-sided 95% CI will be calculated.

[MMRM model]

- Fixed effects: Evaluation timepoint
- Random effects: Subjects

2) Hb at each treatment period timepoint

Descriptive statistics will be calculated for Hb levels at each treatment period timepoint, and analysis performed taking into account changes over time using MMRM.

- 3) Proportion of subjects with mean Hb levels within the target range (10.0–12.0 g/dL), <10.0 g/dL, and ≥ 12.0 g/dL at each timepoint in the treatment period
Numbers and ratios of subjects with mean Hb at each treatment period timepoint within the target range (10.0–12.0 g/dL), <10.0 g/dL, and ≥ 12.0 g/dL will be shown.
- 4) Number of days from the first day of the treatment period required to reach the target Hb range (10.0–12.0 g/dL)
Descriptive statistics will be calculated for days from the first day of the treatment period required to reach the target Hb range (10.0–12.0 g/dL). A Kaplan-Meier plot will be shown for days from the first day of the treatment period required to reach the target Hb range (10.0–12.0 g/dL). Statistical summaries will not include subjects with Hb ≥ 10.0 g/dL on the first day of the treatment period.
- 5) Rate of increase in Hb levels
Descriptive statistics will be calculated for the rate of increase.

(2) Other endpoints

Incidence and ratios will be shown for discrete data, while descriptive statistics will be calculated for continuous data.

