Table 14.2.3.1.1.1	Hb: Change from Baseline in Average of Week 20 and Week 24 (LOCF, FAS)																																																								
Table 14.2.3.1.2.1	Hb: Change from Baseline in Average of Week 20 and Week 24 by MMRM (FAS)																																																								
Table 14.2.3.2.1	Hb: Proportion of Subjects with $\geq 1.0$ g/dL Increase from Baseline (FAS)																																																								
Table 14.2.3.3.1.1	Rescue Therapy: Proportion of Subjects Received ESA (FAS)																																																								
Table 14.2.3.3.2.1	Rescue Therapy: Proportion of Subjects Received Red Blood Cell Transfusion (FAS)																																																								
Table 14.2.3.3.3.1	Rescue Therapy: Proportion of Subjects Received Phlebotomy (FAS)																																																								
Table 14.2.3.4.1.1	Average Dose of Study Drug (FAS)																																																								
Table 14.2.3.4.2.1	Distribution of Dose of Study Drug (FAS)																																																								

Table 14.2.3.5.1 Summary of Dose Adjustments of MT-6548 (FAS)
Table 14.2.3.6.1 Average Dose of Iron: Absolute and Change from Screening Period (FAS)
Table 14.2.3.7.1 Iron Supplementation: Proportion of Subjects Administered Iron Supplementation (FAS)
Table 14.2.3.8.1 Proportion of Subjects with Serum Ferritin <math>\geq</math>100 ng/mL or TSAT <math>\geq</math>20% (FAS)
Table 14.2.3.9.1.1 Serum Iron: Absolute, Change and Percent Change from Baseline (FAS)
Table 14.2.3.9.1.2 TIBC: Absolute, Change and Percent Change from Baseline (FAS)
Table 14.2.3.9.1.3 TSAT: Absolute, Change and Percent Change from Baseline (FAS)
Table 14.2.3.9.1.4 Serum Ferritin: Absolute, Change and Percent Change from Baseline (FAS)
Table 14.2.3.9.1.5 Hepcidin: Absolute, Change and Percent Change from Baseline (FAS)
Table 14.2.3.9.2.1 Serum Iron: Change and Percent Change from Baseline by MMRM (FAS)
Table 14.2.3.9.2.2 TIBC: Change and Percent Change from Baseline by MMRM (FAS)
Table 14.2.3.9.2.3 TSAT: Change and Percent Change from Baseline by MMRM (FAS)
Table 14.2.3.9.2.4 Serum Ferritin: Change and Percent Change from Baseline by MMRM (FAS)
Table 14.2.3.9.2.5 Hepcidin: Change and Percent Change from Baseline by MMRM (FAS)
Table 14.2.3.9.2.6 Serum Ferritin: Absolute by MMRM (FAS)

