The number, proportion, and 95% CI (Clopper-Pearson [Exact] method) of the proportion of subjects per daily dose based on the prescription should be provided at each evaluation time point.

The proportion of subjects per daily dose based on the prescription at each evaluation time point of the treatment period should be provided as a stacked bar graph with the number of subjects in each treatment group as 100%. Stacked bar charts should be separately prepared.

If no prescription is available on the day of each evaluation timepoint of the treatment period, the dose should be based on the immediately before prescription.

(5) Total number of dosage adjustments

The cumulative total number of dose adjustments from the first day of the treatment period to Week 24 of the treatment period should be calculated, and the number, proportion, and 95% CI (Clopper-Pearson [Exact] method) of the proportion of subjects are shown. The number and proportion of subjects by total number of dose adjustments for each scheduled study visit period should be shown. The number, proportion, and the 95% CI (Clopper-Pearson [Exact] method) of the proportion of subjects should be provided for subjects defined below in each period between scheduled study visits and during the entire period from the first day to Week 24 of the treatment period. If a subject is included in more than one definition, the subject should be counted in each definition.

✓ No dose adjustment: No change

With dose adjustment: Dose adjustment, dose increase (Increase), dose decrease (Decrease), drug interruption (Interrupt)

Dose adjustment should include the number of times of increase, decrease, and interruption, and should not count as the increase when it is resumed after interruption.

(6) Iron supplement dosage

The following should be provided according to the 3 categories of oral iron supplement, intravenous iron supplement, and iron supplement (any route).

Descriptive statistics of the mean dose of iron supplement per month should be calculated for the screening period, and after the first day of the treatment period, in each period between scheduled study visits and during the entire treatment period from the first day to Week 24 of the treatment period.

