Descriptive statistics of the change in the mean dose of iron supplement per month from the baseline (mean dose of iron during the screening period) should be calculated, after the first day of the treatment period, in each period between scheduled study visits and during the entire treatment period from the first day to Week 24 of the treatment period. Before and after comparison should be conducted for changes from baseline using the paired t-test. Descriptive statistics should be calculated for the changes.

The dosage of iron supplement should be calculated using the dose as iron.

If no iron supplement is administered, the dose should be tabulated as 0 mg. Subjects who changed the administration route of an iron supplement during the treatment period and subjects who had never received an iron supplement during the treatment period should be excluded from the tabulation.

(7) Proportion of subjects receiving oral, intravenous, or iron supplement (any route)

The number, proportion, and 95% CI (Clopper-Pearson [Exact] method) of the proportion of subjects treated with iron supplement via oral, intravenous, or any route should be provided for screening period, and after the first day of the treatment period, in each period between scheduled study visits and during the entire treatment period from the first day to Week 24 of the treatment period. Before and after comparison should be conducted for changes between baseline (proportion of subjects receiving iron supplements by the aforementioned route in screening period) and each period between scheduled study visits using the McNemar test.

Subjects who have not received an iron supplement are to be subjects who have never received an iron supplement during the relevant period, and subjects who have received iron supplement via oral, intravenous, or any route are to be subjects who have received an iron supplement at least once during the relevant period.

(8) Proportion of subjects with serum ferritin  $\geq 100$  ng/mL or TSAT  $\geq 20\%$ .

The number, proportion, and 95% CI (Clopper-Pearson [exact] method) of the proportion of subjects with serum ferritin levels of  $\geq 100$  ng/mL or TSAT levels of  $\geq 20\%$  should be provided at each evaluation time point of the treatment period. Before and after comparison should be conducted for changes between baseline and each period between scheduled study visits using the McNemar test.

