## 9. Changes in the Statistical Analysis Plan from the Study Protocol

- (1) Mean corpuscular volume and mean corpuscular hemoglobin were added to the other efficacy endpoints.

Reason: Because the importance of mean corpuscular volume and mean corpuscular hemoglobin has increased in the efficacy evaluation from a clinical point of view.

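### The change-in-iron-dose analysis selects subjects on treatment-period iron use, so complete stoppers are dropped while new starters are kept

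*SAP*

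**What the plan says.** Protocol 10.1.2 (7) defines the iron endpoint as a dose per visit period: "Mean weekly dosage will be calculated for each scheduled study visit from the first day of the treatment period" up to Week 24. It belongs to the other endpoints, for which Protocol 13.3.2 (2) plans only this: "Incidence and ratios will be shown for discrete data, while descriptive statistics will be calculated for continuous data".

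SAP 7.5.2 (6) goes further. It reports mean monthly dose for oral iron, intravenous iron and any route. It takes the mean screening-period dose as baseline, calculates the change from it for each visit interval and for the whole treatment period, and adds a test: "Before and after comparison should be conducted for changes from baseline using the paired t-test". A subject given no iron counts as 0 mg. Two exclusions follow. Subjects whose iron route changed during treatment are removed, and "subjects who had never received an iron supplement during the treatment period should be excluded from the tabulation".

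The errata leave this text alone and list the output as an FAS table (Table 14.2.3.6.1, "Average Dose of Iron: Absolute and Change from Screening Period (FAS"). SAP section 9, on departures from the protocol, has a single entry: "Mean corpuscular volume and mean corpuscular hemoglobin were added to the other efficacy endpoints".

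SAP 7.5.2 (7) reports the proportion of subjects on iron in screening and in each interval, with McNemar tests and without these exclusions.

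**The concern.** A before-and-after comparison needs a set of subjects fixed independently of the after value. Here having some iron in treatment is the entry condition, so the outcome chooses its own sample. The largest possible reductions, from some dose to none throughout, cannot enter, while increases from none to some always can unless the route later changes.

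Both patterns can occur. Under Protocol 8.5.2 (1) iron is given to hold ferritin or TSAT above thresholds and may be omitted in subjects who respond poorly to it, and "Investigators/subinvestigators will determine iron supplement dosage and administration route".

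The route-change exclusion also rests on post-baseline behaviour. Its sentence is not confined to the oral and intravenous categories. Read literally, it also removes these subjects from the any-route category, where a switch of route has no bearing on total iron.

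At stake is one table. Under an FAS title it would report a mean change and a p-value for a subset defined by the quantity being tested, and a reader would take it as the change in iron need in the study population.

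**Working it through.** The plan states no figure for this analysis, and the sample size of 20 is a feasibility number (SAP 2.3), so there is nothing to reproduce. The check applies the rule as written.

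**Step 1. The rule by pattern of iron use**

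| Screening | Treatment | Change | Under the SAP rule |
|---|---|---|---|
| Yes | None at any time | minus the screening dose | Dropped |
| No | Yes | plus the treatment dose | Kept, unless route changes |
| Yes | Yes | treatment minus screening | Kept, unless route changes |
| Yes | Part of the period only | 0 mg in later intervals | Kept, unless route changes |
| No | No | 0 | Dropped |

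No rule uses screening iron, and no other section restores the first row.

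**Step 2. Effect on the mean**

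Assumed, not from the documents: all 20 subjects are in the FAS, 8 are on 160 mg/month in screening, *s* of them stop completely, *a* others start at 160 mg, and each continuer changes by *c*.

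- SAP set: [(8 − s)c + 160a] / (8 − s + a)
- Users in either period: [(8 − s)c − 160s + 160a] / (8 + a)
- All FAS: [(8 − s)c − 160s + 160a] / 20

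| Scenario | s | SAP set | Users in either period | All FAS |
|---|---|---|---|---|
| A: a = 0, c = 0 | 0 / 1 / 2 / 4 | 0 each time (n = 8/7/6/4) | 0 / −20 / −40 / −80 | 0 / −8 / −16 / −32 |
| B: a = 0, c = −48 (a 30% cut) | 0 / 1 / 2 / 4 | −48 each time | −48 / −62 / −76 / −104 | −19.2 / −24.8 / −30.4 / −41.6 |
| C: a = 1, c = 0 | 1 | +20 (n = 8) | 0 (n = 9) | 0 |

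Values are in mg/month. Scenario B with one stopper, written out: SAP 7 × (−48) / 7 = −48; users (−336 − 160) / 8 = −62; all FAS −496 / 20 = −24.8.

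In A and B the SAP value does not move however many subjects stop. In B it lies above the either-period value once anyone stops, but below the all-FAS value throughout. The direction therefore depends on the reference set.

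**Step 3. Effect on the p-value**

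Take a common dose D when on iron, 20 subjects and the two-sided 5% level of SAP 7.1.1.

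- *4 stoppers, 4 starters, 4 unchanged, 8 never-users.* The net change is 0. The SAP set has n = 8, four changes of +D and four of 0. Mean 0.50 D; SD = √(8 × 0.25 / 7) D = 0.535 D; SE = 0.535 D / √8 = 0.189 D; t = 2.65; p = 0.033. Users in either period (n = 12) and all FAS (n = 20) both give mean 0, p = 1.0.
- *Fewer switches, equal stoppers and starters.* One of each: +0.09 D, p = 0.34. Two: +0.20 D, p = 0.17. Three: +0.33 D, p = 0.08.
- *4 stoppers, no starters, 10 unchanged, 6 never-users.* The SAP set shows exactly 0. Users in either period show −4/14 = −0.29 D, p = 0.040.
- *No stoppers (4 starters, 8 unchanged, 8 never-users).* The SAP set and users in either period agree at +0.33 D.

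**Step 4. Rejection rate with no net change**

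A simulation of 4,000 trials of 20 subjects assumed 30% never-users, gamma-distributed doses with mean 160 mg/month, and equal chances of stopping completely and of starting. With chances of 0.1, 0.2 and 0.3, the SAP set rejected in about 10%, 31% and 71% of trials. Keeping users in either period rejected in about 5%. The upper settings are extreme and show the mechanism, not an expected size.

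**The case against.** The strongest reply is that items (6) and (7) of SAP 7.5.2 work as a pair: (7) shows who uses iron and (6) shows the dose among users. That is a recognised way to present data with many zeros, and starts and stops are not hidden. This stands for the absolute doses. It does not rescue the change from screening or its t-test, because a subject can be a user in one period and not in the other.

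Second, every magnitude is assumed, and the effect needs subjects who use iron in screening and then none at all in treatment. The same iron rule runs from the first screening day to the end of treatment, so nothing in it prompts stopping at the boundary. This is fair. With no complete stoppers the SAP set and users in either period coincide.

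Third, leaving out never-users changes the target population and is not bias in itself, and the direction depends on the comparator. This also stands. The upward shift is claimed only against users in either period with similar screening doses.

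Fourth, Protocol 13.2 foresees further data-handling rules in the SAP, and the time-to-target table is also labelled FAS although it excludes subjects with Hb of at least 10.0 g/dL on the first treatment day. So the silence of section 9 and the FAS title are matters of transparency, and the conclusion does not depend on them. The time-to-target exclusion does differ in kind, because it uses a baseline value.

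Finally, the any-route reading of the route-change sentence is literal and the SAP is a translation, so the intent may be narrower.

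**Conclusion.** The concern holds: the rule is wrong as written for a change-from-baseline analysis. Complete stoppers are lost and new starters kept, and nothing in the SAP or its errata corrects this. The asymmetry remains whether never having received iron is judged per route or for any iron, which the SAP does not say.

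The real size cannot be determined from the documents. Under the assumptions above, with 8 of 20 subjects on 160 mg/month in screening, each complete stopper moves the either-period mean by −20 mg/month when continuers are unchanged, and the SAP set shows none of it. A false significant increase needs several stoppers and starters: p = 0.033 with four of each.

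The consequence is bounded. Iron dose is an other endpoint in an uncontrolled study of 20 subjects, the primary endpoint is untouched, and no trial decision depends on it. The correction should still be made, because the reported mean change and p-value would not describe the population named on the table.

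**What to change.** - **Any route:** delete both exclusions and tabulate all FAS subjects in Table 14.2.3.6.1, with 0 mg where no iron was given. This follows the FAS rule in Protocol 13.1 and the SAP's own zero-dose rule.
- **Oral and intravenous:** define each set without selecting on treatment-period use alone, for example use of that route in screening or treatment. Say how route changers are counted and state the denominator.
- **Supportive display:** keep the summary restricted to treatment-period users, labelled as such, with its n.
- **Documentation:** list the chosen set in SAP section 9.

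The cost is SAP wording and a rerun of one table. No new data are needed, since Protocol 8.5.4 already has screening-period iron recorded in the CRF. The drawback is that all-FAS mean doses will be lower and contain many zeros, so the number of users must be shown beside each mean.

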3.4 Re-testing/re-screening

(1) Re-testing

Re-testing may be performed during the screening period at the discretion of the investigator/subinvestigator for any subject whose laboratory values (Hb, serum ferritin, TSAT, folic acid, vitamin B₁₂, AST, ALT, and total bilirubin) or BP do not meet the inclusion criteria or meet the exclusion criteria during the screening period.

Subjects with blood pressure measurements on the first day of the treatment period which meet exclusion criteria may be re-tested at the discretion of investigators/subinvestigators, and

processed for treatment period initiation if they no longer meet exclusion criteria.

However, the maximum time from the first day of the screening period to the first day of the treatment period is 6 weeks.

[figure not shown]
(2) Re-screening

For any subject whose laboratory values (Hb, serum ferritin, TSAT, folic acid, vitamin B₁₂, AST, ALT, and total bilirubin), BP, or BP measurements on the first day of the treatment period do not meet the inclusion criteria or meet the exclusion criteria during the screening period, re-screening may be performed if the investigator/subinvestigator considers that the subject may become eligible for the study due to natural course or with drug therapy.

However, re-screening may only be performed once for any given subject.

4. Study design

This is a multicenter, uncontrolled, open-label study.

(1) Screening period

The screening period begins on the first day of the screening period, and ends upon completion of tests required on the first day of the treatment period. Maximum screening period time is 6 weeks. Two visits will be made during the screening period; the first (SV1) is the first day of the screening period. The second screening period visit (SV2) occurs after results from laboratory tests performed on the first day of the screening period have been obtained. Testing may be repeated as necessary.

(2) Treatment period

The treatment period will last from completion of scheduled tests on the first day of the treatment period to completion of blood sampling for haematology tests on the final day of the treatment period (Week 24 of the treatment period or discontinuation of treatment).

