During the treatment period, subjects are to visit the study site on the day of dialysis after a 2-day interdialytic interval; however, if this is difficult, subjects are to visit the study site on the day of dialysis after a 1-day interdialytic interval. After the first day of the treatment period, subjects are to visit the study site every 2 weeks until Week 12 and every 4 weeks after Week 12 to undergo the scheduled test. However, subjects are to visit the study site at shorter intervals as necessary, if excessive increases or decreases in Hb are of concern based on the time course of Hb levels or for hemodialysis.

(3) Follow-up observation period

The follow-up observation period consists of 2 weeks from completion of blood sampling for haematology tests on the final day of the treatment period. The final day of the follow-up observation period is 2 weeks from the completion of blood sampling for haematology tests on the final day of the treatment period, regardless of whether a study visit is made on that day.

Subjects should make study visits as close to the same time as possible during the study period for scheduled tests.

5. Study drug, dosage, and administration

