### 2.2 Study design

Study phase: Phase III

Study type: Confirmatory study

Multicenter, uncontrolled, open-label study

Evaluation time point		Informed consent	Screening period [a]		Treatment period [b]											Final day of the follow-up observation [c]	
			First day	Visit 2	W2	W4	W6	W8	W10	W12	W16	W20	W24	Day of discontinuation			
Item	Visit	First day [b]	SV1	SV2	TV1	TV2	TV3	TV4	TV5	TV6	TV7	TV8	TV9	TV10	TV11	Final day of the follow-up observation [c]	
Permitted range (days)			-	-	-	-3	-3	-3	-3	-3	-3	-3	-3	-3	+7	or +14 [e]	
Procedure/evaluation																	
Informed consent		X															
Inclusion/exclusion criteria		X	X		X												
Patient background and history		X			X												
Height					X						X						
Dry weight, body weight [f]					X									X			
Folic acid and vitamin B 12 [g]					X										X		
Pregnancy tests [i]			X														
Hematology tests [g], [h], [i]		X	X [k]		X	X	X	X	X	X	X	X	X	X	X		
Blood biochemistry tests [g], [h], [i]		X			X	X	X	X	X	X	X	X	X	X	X		
C-reactive protein [g], [h]		X			X										X		
Iron-related measures [g], [h]		X			X	X	X	X	X	X	X	X	X	X	X		
Hepcidin [h]		X			X	X	X	X	X	X	X	X	X	X	X		
EPO [h]		X			X	X	X	X	X	X	X	X	X	X	X		
VEGF[h]		X			X										X		
Vital signs [g], [h], [m]		X			X	X	X	X	X	X	X	X	X	X	X		
Resting standard 12-lead ECG [h], [n]		X			X										X		
Fundoscopy [e]		X			X									X			
Chest X-ray [e]		X			X									X			
Duration of hemodialysis					X										X		
QOL measures (EQ-5D-5L, KDQOL)					X						X						
AE investigation					X	X	X	X	X	X	X	X	X	X	X		
Blood sampling for genetic analysis [o]																X	
Product evaluation/procedure																	
Investigation of concomitant medications/therapies					X	X	X	X	X	X	X	X	X	X	X	X	X
MT-6548 tablets [p], [q]																	
Iron supplements																	
Administered according to the dosage adjustment guidelines																	
Iron supplements administered to maintain serum ferritin values of $\geq 100$ ng/mL or TSAT of $\geq 20\%$																	

- [a] The screening period can be up to 6 weeks. Test results should be reviewed prior to transition from the first day of the screening period to screening period Visit 2 and from screening period Visit 2 to the first day of the treatment period. Re-testing can be performed as necessary.

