#### 4.13 Iron supplement dosage

The dose of iron supplements is defined by the following formula.

Mean monthly dose of iron supplements during the screening period\* and each scheduled study visit period\* (tabulation period of iron supplements) = (Daily dose based on the physician's prescription × Period of administration (days) of the corresponding dose\* during the tabulation period of iron supplements)/Tabulation period of iron supplements (days)\* × 30.4375\*

- \*: The number of days of the screening period is “First day of the treatment period – First day of the screening period”.
- \*2: For each period between the scheduled study visits, the actual study visit dates are not considered, and this tabulation is fixed as follows:
  - The first day of the treatment period to Week 2 of the treatment period: The first day of the treatment period (Day 1) to Day 14
  - Week 2 of the treatment period to Week 4 of the treatment period: Day 15 to Day 28
  - The same shall apply thereafter, and the final period between the scheduled study visits should be Week 20 to Week 24 of the treatment period: Day 141 to a blood sampling day for hematological tests at Week 24 of the treatment period. However, for subjects who discontinued their treatment, the final period between the scheduled study visits should be up to the day before discontinuation.
- \*3: If there are multiple applicable doses, the sum of the calculated values for each dose should be used.
- \*4: For subjects who discontinued their treatment, the final period between the scheduled study visits (days) should be the actual number of days until the day before discontinuation.
- \*5: In this tabulation, 1 month is counted as 30.4375 days ( $365.25/12 = 30.4375$ ).

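### SAP 7.5.2(7) tests at-least-once iron use over periods of unequal length, so unchanged intermittent iron practice can give a significant fall or a significant rise

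*SAP*

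**What the plan says.** SAP 7.5.2(7) reports the proportion of subjects given iron orally, intravenously or by any route. It does so for screening, for each period between scheduled visits and for the whole treatment period. Users are "subjects who have received an iron supplement at least once during the relevant period". The baseline is the "proportion of subjects receiving iron supplements by the aforementioned route in screening period", and it is compared with "each period between scheduled study visits using the McNemar test". The test is named only for the inter-visit periods. The whole-period figure gets a number, a proportion and a Clopper-Pearson interval.

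The lengths of the periods are set elsewhere:

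- **Screening.** The SAP schedule notes (2.2) say "The screening period can be up to 6 weeks", and the Protocol Summary, section 4, says "Maximum screening period time is 6 weeks". SAP 4.13 counts its days subject by subject as "First day of the treatment period – First day of the screening period". No minimum is stated.
- **Treatment.** Visits are "every 2 weeks until Week 12 and every 4 weeks after Week 12" (Protocol Summary, section 4). That gives six 14-day periods and then three 28-day periods, as the footnotes to SAP 4.10 confirm. A discontinued subject's last period is cut short (SAP 4.13).

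For the neighbouring iron dose endpoint, 7.5.2(6), SAP 4.13 divides by the days in the period and multiplies by 30.4375. Item (7) has no comparable step.

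**The concern.** When iron is given intermittently, the chance of at least one dose in a period rises with the length of the period. McNemar's null hypothesis is that the two proportions are equal. With unequal periods, that is not the same as unchanged practice, so part of what the test measures is period length.

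Intermittent use is plausible. Iron is given to keep ferritin or TSAT above a threshold, the investigator chooses dose and route (Protocol 8.5.2), and the SAP tabulates the intravenous route separately. The study has no control arm in which the same artefact would show. A significant fall in the share of subjects on iron could be taken for reduced iron need, and a rise for the opposite.

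**Working it through.** The plan gives no expected result for this endpoint, and its sample size of 20 rests on feasibility (SAP 2.3), so there is no figure to reproduce. The question is how often the test rejects when practice does not change.

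**Inputs from the documents:** at-least-once rule; McNemar's test, two-sided 5% (SAP 7.1.1); 20 subjects; screening up to 42 days; periods of 14 and 28 days.

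**Assumptions:** 12 of 20 subjects are on iron, with a fixed interval *I* and random phase; screening is 14, 21, 28 or 42 days. The SAP does not name the form of the test, so the exact form is used.

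**Formula.** P(at least one dose in *L* days) = min(1, *L*/*I*).

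**Reachability.** If all *k* discordant pairs go one way, exact p = 2 × 0.5^k. Five pairs give 0.0625 and six give 0.031, so six are enough. The asymptotic form without continuity correction needs only four (p = 0.0455).

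**Results for *I* = 28 days:**

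1. *28-day screening, 14-day period.* Screening catches all 12 (60% of 20). The period catches each with probability 14/28 = 0.5 (30% of 20 expected). All discordance is a fall: P(Bin(12, 0.5) ≥ 6) = 2510/4096 = **61%**. Screening of 42 days also catches all 12 and gives the same figure.
2. *21-day screening, adjoining 14-day period.* Per user, P(screening only) = 0.50, P(period only) = 0.25, P(both) = 0.25. Enumerating the trinomial for 12 users gives a false fall in **9%** and a false rise in under 0.1%.
3. *14-day screening, 28-day period.* This mirrors case 1. The period catches all 12 and screening catches half: false rise **61%**.
4. *14-day screening, adjoining 14-day period.* All 12 pairs are discordant, each way with probability 0.5. A split of 10 to 2 or wider is needed: (1 + 12 + 66)/4096 = 1.9% in each direction, which is symmetric and within the nominal level.
5. *28- or 42-day screening, 28-day period.* Both catch all 12: 0%.

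**Other intervals.** With *I* = 21 and 28-day screening against a 14-day period, P(Bin(12, 1/3) ≥ 6) = 17.8%. With *I* of 14 days or less, including daily iron, every period of 14 days or more catches every user: 0%.

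**A second dosing model.** Here doses fall at random times, independently between periods, with mean interval 28 days, and P = 1 − exp(−*L*/28).

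| Screening v period | Share of the 20 on this schedule | Expected use among them | False result, exact test |
|---|---|---|---|
| 42 v 14 days | all | 77.7% v 39.3% | fall, 57% |
| 42 v 14 days | half | 77.7% v 39.3% | fall, 18% |
| 28 v 14 days | all | 63.2% v 39.3% | fall, 21% |
| 42 v 28 days | all | 77.7% v 63.2% | fall, 9% |
| 14 v 28 days | all | 39.3% v 63.2% | rise, 21% |

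**After matching.** With equal lengths (14 v 14 or 28 v 28 days), false rejection in both directions together was at most about 4% (exact) or 5% (asymptotic) in every setting tried, split equally between fall and rise.

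**The case against.** The strongest reply is that the size, and even the sign, rest on quantities the documents do not give. That stands. Six weeks is a maximum, the second screening visit simply follows the first laboratory results, and ESA washout comes before screening and does not lengthen it. Moving from 28 to 21 days of screening takes the false fall from 61% to 9%. A reader might infer that the table is bound to show a spurious drop in iron use. The documents do not support that, because short screening pushes the 28-day periods towards a rise.

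Two more readings go too far. One is that the whole-period figure is also tested against screening; the McNemar sentence covers inter-visit periods only. The other uses 28-day courses and the ratio (28 + 42)/(28 + 14) = 1.67 as if it counted subjects. It counts courses. If 60% of subjects are users in a 42-day screening, a 14-day period catches 1 − 0.4^(42/70) = 42.3%, a ratio of 1.42.

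The way iron is recorded also matters. Protocol 8.5.4 asks for daily dosage and duration of administration. If intermittent iron is entered as one continuing record, the dose-interval model does not apply. The CRF is not available to settle this.

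Finally, item (6) is scaled for time, and ferritin and TSAT are reported throughout. That helps, but item (6) cannot stand in for item (7): it leaves out subjects who changed route and subjects who had no iron during treatment, so anyone who stopped iron at the first dose is missing from it. No document announces a claim about iron need, so the risk is one of misreading.

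**Conclusion.** The point holds as a two-directional defect in one secondary table. Followed exactly, SAP 7.5.2(7) compares unequal exposure windows with a test that assumes they are comparable. If iron is given less often than every 14 days, the false-positive rate can be far above 5%. In the illustration it reaches 61% for a fall or for a rise, depending on screening length. The false fall is mainly a matter for the six 14-day periods, and the false rise for the 28-day periods when screening was shorter than 28 days. These rates rest on assumed dosing intervals, screening lengths and number of users, and on each dose being separately dated. If most iron is daily, or given at fixed intervals of 14 days or less, nothing is distorted. The primary endpoint is unaffected. The change is worth making because it is cheap and there is no control arm to reveal the artefact.

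**What to change.** For the McNemar comparison in 7.5.2(7), use a baseline look-back of the same length as the comparison window. For example, compare the last 14 days before the first dose with each 14-day period to Week 12, and with a 14-day window inside each 28-day period after it. Where a subject's screening or final period was shorter, use the shorter length on both sides. State whether the test is exact or asymptotic.

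The alternative is to drop the test and report item (7) descriptively, with the window lengths in the table. The whole-period figure is already untested and needs no change.

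The cost is SAP wording and one derivation. Protocol 8.5.4 already has screening-period iron recorded in the CRF. The small downside is that iron given outside the matched window is not counted in the test; the full-period proportions can still be shown beside it.
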